Please respond to all components of this item, or clearly indicate which components are not applicable.

Informed consent and all study procedures, other than neuroimaging, will be conducted at BL8.224 or remotely through secure video conferencing software (e.g. Zoom, Teams). Neuroimaging will be done at the AIRC. When informed consent is conducted remotely, DocuSign will be used to obtain signatures. Please see the next page for the assessment schedule.

Methods used to protect privacy: Deidentified data will be stored in REDCap – a self-managed, secure, web-based solution that is designed to support data collection strategies for research studies. Only researchers associated with the study will have access to any protected health information (PHI). This information will not be stored on REDCap. Identifying information will be kept in a separate password-protected file only accessible to the PI and the research team on a need-to-know basis. Data will be analyzed by group, and subjects will be identified only by a subject ID number to protect their confidentiality. Researchers will destroy the personal identifiers upon completion of data collection for the study.

Data analysis plan:

Aim 1: Determine the effect of cortisol on task-driven hippocampal activation using, for the first time, high-resolution (1.5 mm isotropic) fMRI of hippocampal subfields (i.e., DG/CA3, CA1, subiculum). The design is a two-period crossover with randomized order of treatment conditions, and the primary interest is in the treatment effect on hippocampal subfield activation, estimated as the within-subjects difference in hippocampal subfield activation between the hydrocortisone and placebo treatment conditions. The index of hippocampal subfield activation is a beta-weight of the contrast of the task-active condition vs. the control condition (e.g. novel vs. familiar in the Novelty Detection task and lure correct rejections vs. false alarms in the Mnemonic Discrimination task). We will use linear mixed effects regression to estimate the following model of DG/CA3 activation, Y_{ijk} , of the i^{th} subject in the j^{th} group in the k^{th} period, cast in a traditional longitudinal data setup.

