$Y_{ijk} = \mu_i + \beta_c C_{ijk} + \gamma_t T_k + \gamma_c (C_{ijk} - C_{ij0}) + \varepsilon_{ijk}$, where the subject-level mean $\mu_i = \mu + S_i$ is comprised of an overall mean μ and a random subject effect S_i , the time and treatment condition indicators are T_k and C_{ijk} , and ε_{ijk} represents a random residual effect. The corresponding between-subjects sub-model is $Y_{ij0} = \mu_i + \beta_c C_{ij0} + \varepsilon_{ij0}$, where the parameter β_c is identified with the initial condition assignment, which is synonymous with group assignment and therefore represents the carry-over effect. The corresponding within-subjects sub-model is $\Delta Y_{ij} = Y_{ij1} - Y_{ij0} = \gamma_t + \gamma_c (C_{ijk} - C_{ij0}) + (\varepsilon_{ij1} - \varepsilon_{ij0})$, where the parameter γ_c is identified with the change in assigned condition and therefore represents the treatment effect.

Aim 2: Determine the effect of cortisol on hippocampal subfield volume using high-resolution structural MRI. Using the same randomized regression approach described above we will assess mechanistic aim 2.

Aim 3: Assess changes in hippocampal NAA, Glu, Cho and ml with cortisol using ^1HMR S. Similarly, changes in spectroscopy will be assessed using the randomized regression utilized in the previous aims.

Aim 4: Determine the effect of cortisol on declarative and visuospatial memory. We will estimate the treatment effects on declarative memory using the same linear mixed model setup as the primary aim.

Aim 5: Examine whether sex, stress, early life adversity, age, physical activity, GCR number or sensitivity, or changes in sleep during cortisol administration, predict hippocampal CS response, as assessed by memory testing and neuroimaging. We will assess treatment moderation by sex, stress, early life adversity, age, physical activity, and changes in sleep using the modeling setup described in the primary aim with additional terms added to the model. To assess the moderation of a dichotomous variable (i.e., sex), a group indicator (male vs. female) will be added to the regression model (

Form A

IRB # STU 2018-0360

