$Y_{ijk} = \mu_i + \beta_c C_{ij0} + \gamma_t T_k + (\gamma_c + \gamma_{cf} F_i)(C_{ijk} - C_{ij0}) + \varepsilon_{ijk}$, where the overall treatment effect $\gamma_c + \gamma_{cf} F_i$ is allowed to depend on an indicator F_i of sex. For continuous variables, baseline levels will replace the indicator of sex. Continuous moderator analyses will be refined entering and, adjusting for changes in moderators over time by including baseline and longitudinal levels in the model as

$Y_{ijk} = \mu_i + \beta_c C_{ij0} + \beta_q Q_{ij0} + \gamma_t T_k + (\gamma_c + \gamma_{cq} Q_{ij0})(C_{ijk} - C_{ij0}) + \gamma_q (Q_{ijk} - Q_{ij0}) + \varepsilon_{ijk}$. Here, the overall treatment effect $\gamma_c + \gamma_{cq} Q_{ij0}$ is allowed to depend on baseline levels, and the term $\gamma_q (Q_{ijk} - Q_{ij0})$ adjusts for changes from baseline in the within-subjects sub-model.

Aim 6: Explore the effects of cortisol on resting state regional functional connectivity, and whole brain connectomics.

As discussed in the primary aim, the treatment effects on resting state functional connectivity will be assessed using a randomized regression in a traditional longitudinal cast. The key indices of interest will be overall measures of network integrity (e.g., degree, centrality, rich club architecture, etc.).

Aim 7: Explore the impact of depressive symptoms on memory and hippocampal structure, activation, connectivity and 1HMRS outcomes in response to hydrocortisone administration. Depression as a moderator will be assessed similarly to the moderators proposed in aim 5. However, a dichotomous indicator variable representing baseline group assignment (depressed vs. healthy control) will also be included in the model.

Sample size determination:

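### The Aim 5 and Aim 7 moderator models omit the moderator-by-initial-condition term, which shrinks the estimated moderation by a fraction (1−ρ)/2 and costs power.

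*Combined protocol and SAP*

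**What the plan says.** All references are to the combined protocol and SAP, section 4.a.

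- **Aim 1 model.** The subject-level mean "is comprised of an overall mean μ and a random subject effect S_i", so this is a random-intercept model. In the first-period sub-model, "the parameter β_c is identified with the initial condition assignment", and a single value is fitted for everyone. The treatment effect γ_c is attached to the change in condition between periods.
- **Aim 5, sex.** The model is "\mu_i + \beta_c C_{ij0} + \gamma_t T_k + (\gamma_c + \gamma_{cf} F_i)(C_{ijk} - C_{ij0" plus residual. Sex alters the coefficient of the change in condition and nothing else.
- **Aim 5, continuous moderators.** The model contains "\beta_q Q_{ij0} + \gamma_t T_k + (\gamma_c + \gamma_{cq} Q_{ij0})(C_{ijk} - C_{ij0", followed by an adjustment for change in the moderator. It has a main effect of the baseline moderator but no product of that moderator with the initial condition.
- **Aim 7.** "Depression as a moderator will be assessed similarly to the moderators proposed in aim 5", with the addition that "a dichotomous indicator variable representing baseline group assignment (depressed vs. healthy control) will also be included in the model". That is a main effect only.
- **Sample size, Aims 5 and 7.** The plan claims 90% power for moderation by sex with 48 completers at d = 0.68, and treats depression the same way.

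Nowhere does the plan add a moderator-by-initial-condition term, treat subject effects as fixed, or say that moderation will be estimated from within-subject differences alone.

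**The concern.** Nothing precedes the first period, so β_c·C_ij0 carries the first-period treatment effect, although the plan labels it carry-over. If hydrocortisone acts differently in women and men, it does so in the first period as well as the second. The printed model permits the difference only in the second.

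Without a moderator this parameterisation is harmless: β_c is free, and γ_c is estimated from within-subject change. The trouble starts when the moderator is attached to one of the two coefficients and not the other.

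Section 1 names the depressed versus non-depressed and the male versus female comparisons as questions the study is meant to answer. Those coefficients would be biased towards no difference, with intervals centred in the wrong place.

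**Working it through.** **Inputs.** The model terms and random intercept are as quoted above. The design is from Aim 1: "The design is a two-period crossover with randomized order of treatment conditions". Planned completers are 168, and the moderation power claim uses 48 at d = 0.68 (Sample size determination). The plan does not give ρ, the sequence ratio, or α for these tests. I assume 1:1 sequences balanced within moderator level and two-sided α = 0.05, and show a range for ρ.

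**The plan's own figure.** For a contrast of change scores between two groups of 24, with d on the single-measurement SD, the noncentrality is d / [√(2(1−ρ)) · √(4/48)].

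- At ρ = 0.736: 0.68 / (0.7266 × 0.2887) = 3.24, giving 90%. The claim reproduces if ρ is about 0.74.
- With d on the change-score SD: 0.68 / 0.2887 = 2.36, giving 65%. It does not reproduce.
- A paired calculation with n = 24 also comes close: 0.68 × √24 = 3.33, giving 91.5% (normal) or 89.1% (t).

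**Bias.** Let s = C_ij0 (0 or 1) and z = 1 − 2s. Let the true treatment effect be θ + δF in both periods, with no carry-over. Let σ_S² and σ_e² be the subject and residual variances, and ρ = σ_S²/(σ_S² + σ_e²).

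1. *Difference, Y₁ − Y₀.* The truth contains δFz and the model contains γ_cf·Fz. This part estimates δ, with variance proportional to 2σ_e².
2. *Sum, Y₀ + Y₁.* Every subject receives both conditions, so the truth has no Fz term. The model nevertheless contains γ_cf·Fz. This part estimates 0, with variance proportional to 4σ_S² + 2σ_e².
3. Generalised least squares weights the two by inverse variance. The weight on the sum is 2σ_e² / (4σ_S² + 4σ_e²) = (1−ρ)/2. Hence E(γ̂_cf) = δ(1+ρ)/2.
4. The standard error also shrinks, by √((1+ρ)/2). The noncentrality therefore falls by the net factor √((1+ρ)/2).

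Example at ρ = 0.5 and unit total variance: the variances are 1 (difference) and 3 (sum), and the weights are 0.75 and 0.25. The estimate averages 0.75δ, and a noncentrality of 3.24 becomes 3.24 × 0.866 = 2.81, giving 80% power.

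**Range.** Take an effect that the correct model detects with 90% power. At 168 completers this is d = 0.50 in change-score SDs: 0.50 × √(168/4) = 3.24. Coverage of the nominal 95% interval uses bias/SE = 3.24 × [(1−ρ)/2] / √((1+ρ)/2).

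| ρ | Shrinkage | Power as printed | Coverage of true δ |
|---|---|---|---|
| 0.2 | 40% | 71% | 61% |
| 0.3 | 35% | 74% | 71% |
| 0.5 | 25% | 80% | 85% |
| 0.7 | 15% | 85% | 92% |
| 0.736 | 13% | 85.5% | 93% |
| 0.8 | 10% | 87% | 94% |
| 0.9 | 5% | 88.5% | 95% |

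**Does the main effect alone help?** No. In the exact calculation with 42 per sex-by-sequence cell, the retained fractions at ρ = 0.2, 0.3, 0.5, 0.7 and 0.8 are 0.60, 0.65, 0.75, 0.85 and 0.90, with or without F. Adding F and F × C_ij0 gives 1.00 throughout.

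**Simulation check.** REML fits, binary moderator, 168 subjects, 1,500 trials per setting:

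| ρ | Estimate/truth, main effect only | Power | Estimate/truth, with F × C_ij0 | Power |
|---|---|---|---|---|
| 0.3 | 0.651 | 73.5% | 0.996 | 89.3% |
| 0.5 | 0.755 | 80.3% | 1.003 | 90.1% |
| 0.736 | 0.867 | 85.6% | 0.999 | 89.3% |
| 0.9 | 0.956 | 88.7% | 1.007 | 90.1% |

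Fitting the sex equation exactly as printed, without the main effect, and simulating a sex difference of 0.3 SD, the ratios are 0.680, 0.773, 0.874 and 0.958. They are slightly higher because the fitted model then overestimates ρ.

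**The case against.** The strongest case on the other side has four parts.

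- **Scope.** The Aim 1 treatment effect has no moderator and is untouched, as are Aims 2 to 4 and 6. Aim 7 is labelled exploratory. When there is no true moderation the coefficient is unbiased, so no spurious interaction is created. All of this is right. But Aim 5 is a clinical aim, and section 1 poses the sex and depression comparisons as study questions.
- **Power at the planned effect.** At 168 completers and d = 0.68, the printed model keeps 94% power at ρ = 0.3 and 97% at 0.5 if d is on the change-score SD, against 99% with the term. On the single-measurement SD the figures are 85% against 96% (ρ = 0.3) and 97% against 99% (ρ = 0.5). So the power loss at that effect is often small. At d = 0.34 on the single-measurement SD it is larger: 48% against 60% at ρ = 0.5, and 81% against 86% at ρ = 0.736. In every case the estimate remains biased, and a larger sample does not change that.
- **Value of ρ.** The plan's 90% claim is consistent with ρ near 0.74, where the shrinkage is 13%; the low-ρ rows have no direct support. That is fair, and it is why a range is shown. But the same model is applied to activation, volume, spectroscopy, memory and connectivity, and ρ is justified for none of them.
- **Intent.** Aim 1 describes the treatment effect as a within-subject difference, and moderation estimated from those differences alone would be unbiased. The specified fit, however, is a random-intercept mixed model, which does not restrict itself to those differences.

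**Conclusion.** The concern holds. As written, the models for moderation by sex, continuous baseline measures and depression estimate δ(1+ρ)/2 rather than δ. For ρ from 0.2 to 0.9 the shrinkage runs from 40% to 5%, and 90% power falls to between 71% and 88.5%. At the ρ that reproduces the plan's own claim (48 completers, d = 0.68), the shrinkage is 13% and power is 85.5% rather than 90%.

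The result assumes a random intercept, complete data, sequence balanced within moderator level, and no carry-over that depends on the moderator. The numerical checks used a binary moderator. The continuous-moderator equation lacks the same term, but the exact fraction has not been shown for change in sleep, which is measured after randomisation. The bias in the reported moderation matters more than the power loss. It should be corrected before analysis.

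**What to change.** Add the missing product to every Aim 5 and Aim 7 model:

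- sex: F_i and F_i × C_ij0;
- continuous moderators: Q_ij0 × C_ij0 (the main effect is already there);
- depression: depression × C_ij0 (the main effect is already there).

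Keep γ_cf (or its counterpart) as the test of moderation. An alternative is μ_i + γ_t·T_k + τ·C_ijk + φ·F_i + δ·F_i·C_ijk, testing δ. It gives the same δ with complete data, but it drops the plan's initial-condition term, and with dropouts its precision differs slightly. A regression on within-subject differences alone would also be unbiased.

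The cost is one or two degrees of freedom per model and a revision of the equations, with no new data. The plan should also state the ρ and the SD scale behind the moderation power claim, so that it can be checked against the corrected model.

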Electrocardiogram (ECG)	X		X		X
Urine pregnancy test (UPT)	X		X		X
Randomization			X		
Begin 3-day course of hydrocortisone or placebo			X		
Begin 3-day actigraphy monitoring			X		
Structural and functional MRI, spectroscopy			X		X
Follow-up with a clinician			X		X
Adverse events review			X		X
Exit survey			X		X
Approximate time/visit	3 hr	45 m	3.5 hr	45 m	3.5 hr

Form A

IRB #	STU 2018-0360
-------	---------------

4.b. List of the study intervention(s) being tested or evaluated under this protocol

	N/A - this study does not test or evaluate an intervention. Skip to item 4.d.		
#	Study intervention(s) being tested or evaluated under the protocol Add or delete rows as needed	Affiliate Place a check next to institution(s) where the intervention will be performed	Local Standard Practice? Indicate whether the intervention is considered acceptable practice locally for applicable institutions
1	Hydrocortisone	 UTSW	 Yes
		 PHHS	 Yes
		 CMC	 Yes
		 THR	 Yes
		 TSRH	 Yes
		 Other: _____	 Yes

4.c. Risk:Benefit Analysis of study interventions being tested or evaluated under this protocol

For each study intervention identified in section 6b above, complete a risk:benefit analysis table.

(Two tables are provided, copy & paste additional tables as needed or delete both tables if this study does not test an intervention)

Form A

IRB #	STU 2018-0360
-------	---------------

4.c.

Study Intervention #1

Hydrocortisone

List each group exposed to this intervention on a separate line. (e.g., experimental, control, Arm A, Arm B, etc) Or state All Groups/Subjects
	
For each group, list the benefits of this intervention. (Benefits can be directly from the intervention or from a monitoring procedure likely to contribute to the subject's well being). If there are no benefits, state "none".

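### Aim 5 asks about change in sleep, but the moderator rule ties the treatment effect to a baseline sleep level, and the coefficient that carries sleep change is labelled an adjustment

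*Combined protocol and SAP*

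**What the plan says.** All references are to the combined protocol and SAP.

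- **The question.** In the item 4.a data analysis plan, Aim 5 asks whether "changes in sleep during cortisol administration, predict hippocampal CS response". The modelling sentence repeats it: "We will assess treatment moderation by sex, stress, early life adversity, age, physical activity, and changes in sleep".
- **The rule.** The model for sex lets the treatment effect be γ_c + γ_cf F_i. Then: "For continuous variables, baseline levels will replace the indicator of sex". Sleep is not exempted.
- **The refinement.** The next sentence refines the continuous analyses by "adjusting for changes in moderators over time by including baseline and longitudinal levels in the model". The printed model has treatment effect γ_c + γ_cq Q_ij0, plus a term γ_q (Q_ijk − Q_ij0). The plan says that this last term "adjusts for changes from baseline in the within-subjects sub-model".
- **The time index.** Under Aim 1, "The design is a two-period crossover with randomized order of treatment conditions". The sub-models there use subscript 0 for the first period and 1 for the second.
- **The sleep measure.** The Assessment Schedule row "Begin 3-day actigraphy monitoring" sits with the start of the drug course. Table 4.d lists 3-day actigraphy under Visits 2 and 4, again beside the drug course. Neither lists it at Visit 1.

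**The concern.** The predictor named in the aim is a change. The only coefficient that the plan describes as making the treatment effect vary, γ_cq, multiplies a level. For age, PSS-10, CTQ and IPAQ a baseline level is the right variable. For sleep it is a different variable from the one in the aim, and no pre-treatment sleep value is documented to supply it.

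Two coefficients in the refined model could be offered as the sleep result, they mean different things, and the plan does not say which one answers the question. An analyst who applies the moderation rule literally reports γ_cq, whose meaning for sleep depends on treatment order. An analyst who reports γ_q instead is using a term that the plan presents as a covariate. That choice should not be left until the data are seen.

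**Working it through.** **1. The plan's own figure.** No power is given for sleep. The only Aim 5 figure, under Sample size determination, is 90% for moderation by sex with 48 completers and d = 0.68. With noncentrality d√(N/2) = 0.68 × √24 = 3.33 and two-sided α = 0.05 (assumed), power is Φ(3.33 − 1.96) = 0.915, or 0.891 with the t distribution. The figure is reproduced on that formula (a plain 24 v 24 comparison gives 0.654). It neither supports nor refutes anything about sleep.

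**2. What Q_ij0 records if it is first-period sleep.** Illustrative values in minutes:

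| Participant | Placebo | Hydrocortisone | Change | Q_ij0 |
|---|---|---|---|---|
| A, hydrocortisone first | 420 | 360 | −60 | 360 |
| B, placebo first | 420 | 360 | −60 | 420 |
| C, placebo first | 420 | 420 | 0 | 420 |

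A and B have the same change and different scores. B and C have different changes and the same score.

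**3. Which coefficient carries the change.** Let s = C_ij1 − C_ij0 (+1 for placebo first, −1 for hydrocortisone first). Let R = s(Y_ij1 − Y_ij0) be the response and D = s(Q_ij1 − Q_ij0) the sleep change on hydrocortisone against placebo. Multiplying the refined within-subjects sub-model by s gives

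R = s γ_t + γ_c + γ_cq Q_ij0 + γ_q D + error.

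So γ_q is the slope of response on sleep change, and γ_cq is not. For A, D = −1 × (420 − 360) = −60. For B, D = 360 − 420 = −60. For C, D = 0. This step needs no assumed figures.

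**4. Size, by simulation with 168 completers.** The documents give no sleep figures, so three sets of assumptions were used.

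- *Set 1*: within-subject regression, 1,000 runs per setting. The link was set so that a direct test has about 90% power: r = tanh((1.960 + 1.282)/√165) = 0.247. SD of sleep change over SD of placebo sleep was 0.5 or 1, and their correlation 0, −0.3 or −0.6. Q_ij0 was either pre-treatment or first-period.
- *Set 2*: r = 0.3, GLS with compound symmetry, first-period Q_ij0, 2,000 runs per scenario. Between-person sleep SD 45–60 min, SD of change 30–45 min, measurement SD 15–20 min, within-person outcome correlation 0.4–0.7.
- *Set 3*: r = 0.3, assumed sleep SDs, including a negative correlation between usual sleep and sleep change.

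Percentage of runs in which the link is detected:

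| Coefficient | Set 1 | Set 2 | Set 3 |
|---|---|---|---|
| γ_cq, simple baseline model | 4–41 | 7–24 | 8–18 |
| γ_cq, refined model | 4–7 | 4–7 | 4–9 |
| γ_q, refined model | 76–90 | 79–87 | 74–90 |
| Sleep change as moderator | 88–90 | 89–93 | 81–94 |

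With no link, all four reject in 4.6–5.6% of runs (set 2). In set 1, γ_cq in the simple model averages between −0.47 and +0.34 against a true slope of 1. The highest rejection rates (38–41%) come with a pre-treatment baseline and correlation −0.6, where its sign is opposite to the sleep-change slope. With 48 completers and r = 0.447, γ_cq in the simple model detects the link in 5–36% of runs and γ_q in 77–90%.

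**5. Hand check on the last row.** In set 2 the direct slope is 66–73% of the true one because sleep is measured with error. A slope factor λ shrinks the correlation by √λ: 0.3 × √0.66 = 0.244 and 0.3 × √0.73 = 0.256. Power is Φ(√165 × atanh(r) − 1.96), which gives 0.89 and 0.92, in line with 89–93%.

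**6. Why γ_q is smaller in the mixed model.** In the within-subject regression γ_q averages 0.99–1.01. In a random-intercept mixed model with first-period Q_ij0 it averages about 0.83–0.85, and in set 3 it is about 14–26% below the direct estimate. The first-period part of the refined model contains C_ij0 and Q_ij0 but not sleep change by condition. A hydrocortisone-first participant's first-period outcome does depend on that product, and the misfit passes into γ_q through the correlation between the two equations.

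**The case against.** The strongest reply is that the quoted rule is only a first step. The refined model follows at once and contains the change term. Of the continuous moderators in the modelling sentence, PSS-10, CTQ and IPAQ are scheduled at Visit 1 only and age is not a repeated measure, so sleep is the one for which Q_ijk − Q_ij0 carries data. The natural reading may be that this term is how sleep change enters. Fitting the model as written yields γ_q, with power not far below that of a direct test.

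Most of this stands. A reader might infer that the plan leaves sleep change out, or that a real link would usually be missed. The documents do not support either: the change is in the printed model, and nothing says that γ_cq will be reported as the sleep-change result. The poor detection rates belong to γ_cq alone.

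What the reply does not answer is that the plan promises moderation by sleep change, writes the treatment effect as a function of Q_ij0 only, and gives γ_q the role of a covariate. Nor does it supply a sleep baseline. Reading Q as the sleep change itself does not help, because a change within the trial has no baseline level.

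The schedule as extracted shows a single mark for actigraphy. That may come from a broken table, and no weight is placed on it.

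**Conclusion.** The point holds in a limited form. For sleep, the stated moderation coefficient answers a different question from the one in Aim 5. The coefficient that does answer it is in the refined model but is not named as the result, and Q_ij0 for sleep is undefined.

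The practical loss depends on what is reported. With γ_cq, detection is about 4–9% in the refined model and 8–18% in the simple one, rising to about 40% or changing sign with the assumed correlation between usual sleep and sleep change. With γ_q it is about 74–90%, but the mixed-model estimate is some 14–26% too small relative to a direct one. The algebra is free of assumptions once Q_ij0 is read as the first-period value. Every percentage rests on assumed sleep SDs, correlations, link strength and α = 0.05 two-sided.

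This affects one predictor in Aim 5 and leaves the Aim 1 treatment-effect analysis untouched. It should be corrected before analysis because the correction is cheap.

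**What to change.** Exempt sleep from the baseline-level rule and keep that rule for age, PSS-10, CTQ and IPAQ. Define D_i as actigraphy sleep during the hydrocortisone course minus sleep during the placebo course, centred, and fit

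Y_ijk = μ_i + β_c C_ij0 + β_d D_i + β_cd D_i C_ij0 + γ_t T_k + (γ_c + γ_cd D_i)(C_ijk − C_ij0) + ε_ijk.

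Report γ_cd as the Aim 5 sleep result. Describe it as an association, because D_i is measured after randomisation. The D_i × C_ij0 term is what removes the shrinkage in step 6. At minimum, state that γ_q is the sleep-change result and define Q_ij0 for sleep.

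The cost is one sentence and one model line. No new data are needed if the table 4.d listing under Visits 2 and 4 means that actigraphy accompanies both courses; that listing and the Assessment Schedule should be reconciled. Participants without actigraphy in both periods drop out of this one analysis.
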